**Participant privacy:**

Privacy language is included in the informed consent form. Participants must be willing to allow the sharing of information between the research team and their regular mental health and primary care providers. Participants have the option of withdrawing from the study at any time and can request that no further information be shared about them from that point on. Data that were collected prior to their withdrawal will be de-identified and will still be used in the data analysis for the study.

**Data confidentiality**

The study personnel at UHCMC whose responsibilities require access to personal data agree to keep the identity of study subjects confidential. Study data will be collected and managed using REDcap (Harris et al., 2009), a secure, web-based application designed to support data capture for research studies.

Careful attention will be given to confidentiality, which will be maintained using subject identification (ID) codes. Study ID codes will be the basis for linking information from data and results. Audio recordings will be assigned their respective subject code. Research files are not available to any unauthorized person. The list that links

study ID codes with subject names and all forms bearing subject names will be stored in a password protected file in a folder only accessible to research team personnel on the secure UH server.

A Certificate of Confidentiality has been secured from NIMH by the investigators.

**Data security:**

Research files are not available to any unauthorized person. Research data are collected and stored using UH REDCap. Any paper assessment forms are stored in file cabinets in the locked research offices of the PI on the 7th floor of the W.O. Walker Center at [name]. The list that links study ID codes with subject names and all forms bearing subject names will be stored in a password protected file in a folder only accessible to research team personnel on the secure UH server and/or REDCap. Data analysis files will also be stored in the secure folder on the UH network.

Data Safety and Monitoring will be the responsibility of 1) The study's principal investigator ([name]), 2) The local Institutional Review Board (IRB), and 3) a DSMB.

With regard to loss of confidentiality associated with the mobile device, no personally identifying information will be texted by the study team or stored on the device unless the participant chooses to do so. Therefore, if a device is misplaced, there is minimal likelihood that any loss of confidential information will occur.

Adverse events will be assessed and recorded at every visit following the Screening visit. Assessments will include observations by investigators, spontaneous reporting by subjects, and standard non-leading questions. For every adverse event, the PI will provide an assessment of the severity, duration and causal relationship to study intervention, and document all actions taken with regard to study intervention, as well as any other treatment measures for the adverse event. If an outcome for an adverse event is not available at the time of initial report, follow-up will proceed until the outcome is known.

For the purposes of this investigation, a serious adverse event will be defined as any untoward medical occurrence believed to be possibly or probably due to the study and:

1. Results in death
2. Is life threatening
3. Results in persistent or significant disability
4. Is a congenital anomaly
5. Is an important medical event that may not be immediately life threatening or results in death or hospitalization

If serious and unexpected adverse events occur, or any other unanticipated problems involving risks to subjects or others, the IRB will be notified. This notification will indicate what serious adverse events were noted, whether they appeared related to the trial, and whether the trial was approved to continue. If found to be related to the trial, the PI will institute appropriate procedures, notify the NHLBI Project Officer, and report such events to appropriate institutional officials and the Office for Human Research Protections.

**Data Analysis plan:** The aim of this project is to test the use of iTAB-CV in a pilot feasibility, acceptability and preliminary efficacy study in a sample of 38 individuals with BD and HTN. Hypothesis: iTAB-CV will be feasible to conduct in an outpatient setting, will be acceptable to participants, and will be associated with improved HTN medication adherence among at-risk individuals with BD and HTN. Treatment acceptability/satisfaction will be measured via a self-report questionnaire and feasibility will be evaluated by percentage of texts answered. The primary dependent measure will be treatment adherence of antihypertensives evaluated with Tablets Routine Questionnaire (TRQ). Adherence will also be measured objectively through eCAP. The measurements will be taken at screening, baseline (4 weeks), 8 weeks, and 12 weeks follow-up. Of primary inferential focus is whether there is change in adherence from baseline to 12 weeks. Adherence will be calculated as a proportion of prescribed medications taken in the past week and will be assessed for each regularly scheduled maintenance agent for HTN prescribed for three months or longer on a daily, routine basis. For individuals who are on more than one such agent, adherence will be assessed for each agent and an average will be

calculated. TRQ will be the main adherence measure, but eCAP will also be analyzed and compared with the TRQ. Secondary outcome measures are: Systolic blood pressure, TRQ for antipsychotic and/or mood stabilizers, psychiatric symptoms (BPRS health utilization, Medication Adherence Self-Efficacy Scale - Revised, Self-Report Habit Index (64), Brief Illness Perception Questionnaire, Beliefs About Medicines Questionnaire, AMSQ, treatment acceptability/satisfaction by questionnaire and exit interviews, and feasibility via % texts answered.

Main Hypothesis Testing: A paired t-test will be used to test significance for the TRQ and eCAP adherence outcomes from baseline to 12-week follow-up. Nonparametric tests will also be considered. Secondary Hypothesis Testing: Difference from baseline to 8 weeks, and 8 weeks to 12 weeks will also be analyzed. Corresponding TRQ and eCAP values will be correlated and Bland-Altman plots will be used to help identify discrepancies. Correlations will be computed for change in antihypertensive adherence values versus changes in TRQ for antipsychotic and/or mood stabilizers, medication attitudes, self-efficacy, and habit strength. Exploratory longitudinal mixed models will be used to analyze repeated measurements at baseline, 8 weeks, and 12 weeks. Note that the preliminary analyses and model estimates will inform the future design of a more extensive study involving a controlled trial.

Attrition Analyses: Preliminary analyses will determine factors that are associated with attrition effects. Attrition rates in a current BD adherence study at our institution is < 30%. Differential attrition by key covariates such as age and gender will be examined, such as through log rank tests. Power Analysis: Given the preliminary data from a prior BD adherence study (35), difference in oral medication adherence after treatment was 21.7%. Standard deviation of this difference was 39%, resulting in an effect size of 0.56. We expect to observe a similar if not greater effect size. Using a t-test of difference between baseline and 12 week TRQ, power is 0.80 at two-sided alpha = 0.05 for a sample of 38 subjects to reject a null hypothesis of no change in adherence when effect size is 0.549, and attrition is 25%. The projected sample size should thus provide adequate power to detect expected changes in anti-hypertensive drug adherence levels.

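### The serious adverse event definition requires study-relatedness, which conflicts with the reporting paragraph after it and leaves serious events judged unrelated outside the SAE trigger for IRB notice

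*Combined protocol and SAP*

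**What the plan says.** The safety rules stand at the end of the Data security section of the combined protocol and SAP, just before the Data Analysis plan.

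- **Recording.** "Adverse events will be assessed and recorded at every visit following the Screening visit". Each event is then assessed: "For every adverse event, the PI will provide an assessment of the severity, duration and causal relationship to study intervention". No other causality assessor is named.
- **Definition.** For this study, a serious adverse event is "any untoward medical occurrence believed to be possibly or probably due to the study and" meeting one of five outcomes. The first is "Results in death". The fifth, the only one to mention hospitalisation, reads "Is an important medical event that may not be immediately life threatening or results in death or hospitalization".
- **Reporting.** "If serious and unexpected adverse events occur, or any other unanticipated problems involving risks to subjects or others, the IRB will be notified". On content: "This notification will indicate what serious adverse events were noted, whether they appeared related to the trial". Notice to the funder's project officer, institutional officials and the federal human-research office follows only where the event is found to be related.
- **Oversight.** The PI, the IRB and a DSMB share responsibility for data safety and monitoring. The section does not say what the DSMB receives or when.

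**The concern.** Seriousness describes the outcome of an event; relatedness is an opinion about its cause. The definition joins them with an *and*, so the opinion on cause has to be formed before an event can be called serious. A death judged unrelated then fails the definition even though death is the first outcome listed.

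This matters in this population. The section on risks acknowledges that participants are already at risk of depression and possible suicidality. Everyone enrolled has hypertension, and physical illness is not a ground for exclusion. A death, suicide attempt or admission can easily be put down to the underlying illness. With a single cohort and no concurrent control, attributing individual events is especially uncertain, so the serious-event listing should not depend on that attribution. The Data Analysis plan also says that the results will inform a later controlled trial, which would inherit an incomplete SAE count.

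**Working it through.** No figure in the plan bears on this point, so the check compares the texts.

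**Step 1. Apply the definition to an event with a listed outcome.**

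| PI's view of cause | SAE under the definition? | SAE trigger for IRB notice | What else catches it |
|---|---|---|---|
| Possibly or probably due to the study | Yes | Met if also unexpected | Adverse event record; further reporting if found related |
| Unrelated | No | Not met, because the event is not an SAE | Adverse event record; IRB notice only if it counts as another unanticipated problem |

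The second row is the gap. The outcome is the same in both rows, and only the causal opinion differs.

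**Step 2. Apply the reporting paragraph to the same event.** The IRB notice is to say whether the SAEs appeared related, and extra steps apply only if a relation is found. Both provisions assume that an SAE may turn out to be unrelated. Under the definition, every SAE is already believed to be at least possibly related, so an event believed unrelated from the start can never appear in such a notice. The two texts disagree on whether an unrelated SAE can exist.

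**Step 3. Read the fifth criterion.** As written, it covers an important medical event that either may not be immediately life threatening or leads to death or hospitalisation.

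- Death is then listed twice, here and in the first criterion.
- Hospitalisation counts only if the event is also judged an important medical event.
- A reader could instead take the sentence to mean that such an event need not be life threatening or lead to death or admission. Hospitalisation would then not be a criterion at all.

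Two people could classify the same psychiatric admission differently.

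**Step 4. Check whether other provisions close the gap.**

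- Adverse event recording captures the event but does not send it to the IRB.
- The unanticipated-problems trigger could send it, but the term is not defined here. It does not clearly reach an admission for mania or depression that is judged unrelated.
- Hospitalisation and emergency care are collected under Additional Measures as health resource use, which is an outcome measure and not a safety report.

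Each provision reduces the loss. None makes the event an SAE.

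**The case against.** The best case for the plan has four parts.

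1. **The reporting paragraph shows the intent.** It expects notices to state relatedness, so staff may well report unrelated serious events. The texts can also be read as two stages: a low initial threshold of possible relation, then a later finding. This stands in part. It gives the later finding some meaning, but an event judged unrelated at the outset is still excluded.
2. **Nothing is lost from the data.** All adverse events after screening are recorded with severity, duration and causality, and followed until the outcome is known. Hospitalisations are also counted independently of any causal opinion. Acute risk of harm goes at once to the clinician and the PI, whatever the label. This stands, and it limits the consequence to classification and reporting.
3. **The IRB has a second trigger**, and the first requires the event to be unexpected as well as serious. This stands. Admissions regarded as expected would not meet the SAE trigger even after the definition is corrected, so the change in IRB notices may be smaller than the change in the SAE listing.
4. **The stakes are modest.** This is a 38-person study of text messages added to usual care. The section on pregnant women describes the risk as no more than minimal, and no efficacy analysis or stopping rule depends on the SAE count. This stands and bears on priority, but it does not justify keeping two texts that disagree.

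**Conclusion.** The point holds as a conflict within the safety section. Taken literally, the definition excludes deaths and hospitalisations that the PI judges unrelated, both from the SAE category and from the SAE trigger for IRB notice. The reporting paragraph assumes that such SAEs can exist. The unclear placing of hospitalisation makes the classification less reliable still. The conclusion rests on a literal reading of the definition and on the PI being the only named causality assessor.

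No numerical size can be given. The documents contain no event rate, and any count of affected admissions would rest on an assumed rate and would have to allow for the unexpectedness condition.

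A reader might go further in four ways that the documents do not support:

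- **That unrelated serious events are never counted or reported, or that a pattern among them could not be detected.** They are recorded as adverse events, admissions are also counted as resource use, and the unanticipated-problems route to the IRB remains open.
- **That the DSMB sees a filtered count.** Nothing limits it to SAEs. What it receives is simply not stated, which is a separate gap.
- **That lack of blinding is the cause.** In a single cohort where everyone is treated, there is no allocation to conceal. The relevant fact is that one named role judges causality.
- **That the fifth criterion omits hospitalisation outright.** It names it, but unclearly.

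The correction should be made. It is proportionate for a small pilot because it changes wording only.

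**What to change.** Reconcile the definition with the reporting paragraph as follows.

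1. Delete the causal clause from the SAE definition, so that it runs directly from the untoward medical occurrence to the list of outcomes.
2. List hospitalisation as a criterion of its own, and reword the important-medical-event item so that it stands apart and no longer repeats death.
3. Keep relatedness as a separately recorded judgement for every event, and let it govern the further reporting steps already set out after IRB notice.
4. State that all SAEs will be tabulated regardless of relatedness, with the relatedness judgement shown alongside.

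The cost is a protocol wording change and a slightly longer SAE listing. No visits, staff, procedures or participants are added, and the efficacy analyses are unaffected.

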The Attitude-Social Influence-Efficacy (ASE) model (De Vries & Mudde, 1998) frames adherence to medication as deriving from attitudes (A), social influence (S), and self-efficacy (E). However, adherence also requires intact prospective memory, the ability to remember to do a behavior in the future, which tends to be impaired in those with BD (Bogner, de Vries, O'Donnell, & Morales, 2013; Lee et al., 2010; Zogg, Woods, Saucedo, Wiebe, & Simoni, 2012). Given this deficit, even when an individual has the intention to take medication, they lack the planning or organizational abilities to do so consistently (Zogg et al., 2012). Thus, in order to change and sustain medication adherence in this and similar populations, one must address both ASE and prospective memory. This m-Health intervention primes habit formation by targeting behavioral intention using customized psychoeducational and motivational texts with social reference followed by contextual cues, reminders, and immediate positive reinforcement, to create a strong and automatic habit of taking medication which will be sustainable despite variability over time in behavioral intent.

[figure not shown]

Figure 1: Diagram of expanded ASE model

This study aims to test the feasibility, acceptability and effectiveness of a customized m-Health texting intervention built on the Individualized Texting for Adherence Building (iTAB) platform on antihypertensive adherence and systolic blood pressure in hypertensive persons with BD. This practical, customized intervention, intended to improve adherence to antihypertensives and BD medication among high risk individuals, will be suitable for implementation in either primary care or mental health settings and may reverse the unacceptably high morbidity and mortality in this population.

This study has one specific aim:

**Specific Aim 1:** To test the acceptability, feasibility and effectiveness of iTAB-CV to improve adherence to antihypertensives based on self-reported Tablets Routine Questionnaire (TRQ) and a medication event monitoring system (eCAP).

**Hypothesis 1:** iTAB-CV will improve adherence to antihypertensives in non-adherent persons with BD and HTN.

**Hypothesis 2:** Participants will respond to at least 75% of text messages.

**Hypothesis 3:** At least 75% of participants will find iTAB-CV acceptable based on exit interviews.

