Stage two of iTAB-CV includes the addition of customized context cues/reminders and immediate reinforcement for medication taking behavior in addition to 1 daily motivational mood rating. The number of texts per day will be determined based on the number of times a day that medications are prescribed (up to four a day). Assessments that include evaluation of treatment adherence, psychiatric symptoms, health status, self-efficacy for medication taking behavior, illness beliefs, medication attitudes, and habit strength for both antihypertensive and BD medications will be conducted at four time points over a 3-month time period (screening, baseline/week 4, week 8, and week 12). Blood pressure and weight will be measured at each of the four contacts. Height will be measured at screen. Individuals who drop out of the intervention, and who agree, will be followed up with outcomes assessments over the same 3-month time period that they would have been evaluated had they remained in the study. Table 1 outlines the study schedule of events/assessments.

Individuals will receive reminder telephone calls or text messages during the 2 weeks prior to their scheduled appointment. Individuals will be requested to provide three additional contacts who may assist in facilitating contact with the participant should the individual miss follow-up appointments and if difficulty arises in contacting the individual to re-schedule follow-up (for example, change of address or telephone number). In order to optimize study retention, study staff will maintain personal contacts with study participants via greeting/post cards for birthdays and holidays and regular contact for "location checks" between assessment periods.

One month post study completion, the PI or research study staff will call the individual and will administer the TRQ over the phone for bipolar and blood pressure medications.

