**Table 1: Schedule of Assessments and Study Events**

Procedure	Screen	Baseline	Visit 1	Visit 2
Visit Timing	Day 0	Week 4	Week 8	Week 12
Informed Consent	X			
Inclusion/Exclusion	X			
Demographics, Charlson, medical history	X			
Diagnosis: Mini-International Neuropsychiatric Interview	X			
Prospective Memory: The Memory for Intentions Screening Test (MIST)	X			
Rapid Estimate of Adult Literacy in Medicine – Short Form (REALM-SF)	X			
Brief Illness Perception Questionnaire (Brief IPQ)	X		X	X
Medication Adherence Self-Efficacy Scale - Revised (MASES-R)	X		X	X
Medication Attitudes – Beliefs About Medicines Questionnaire, AMSQ	X		X	X
Self-Report Habit Index	X	X	X	X
Primary outcomes:				
Average TRQ for antihypertensive agents	X	X	X	X
eCAP for antihypertensive agent		X	X	X
Secondary outcomes:				
Systolic Blood Pressure	X	X	X	X
Height (Screen only) and weight / BMI	X	X	X	X
Average TRQ for bipolar medications	X	X	X	X
Brief Psychiatric Rating Scale (BPRS)	X	X	X	X
Montgomery-Åsberg Depression Rating Scale (MADRS)	X	X	X	X
Young Mania Rating Scale (YMRS)	X	X	X	X
Introduction of eCAP for antihypertensive	X			
Brief powerpoint presentation providing psychoeducation on hypertension and bipolar disorder		X		
iTAB-CV interview and training; iTAB-CV stage 1 - initiation of behavioral priming via text + daily mood monitoring; phone given at this time		X		
iTAB-CV stage 2 – brief interview regarding iTAB-CV; frequency of text; choose stems for reminders and reinforcement			X	
Participant acceptability/satisfaction/feasibility/exit interviews				X

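### The main H1 test drops everyone without a week-12 value and has no missing-data sensitivity analysis, and H3's 75% target has no defined denominator

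*Combined protocol and SAP*

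**What the plan says.** **H1.** Under Main Hypothesis Testing in the Data Analysis plan: "A paired t-test will be used to test significance for the TRQ and eCAP adherence outcomes from baseline to 12-week follow-up". Under Secondary Hypothesis Testing: "Exploratory longitudinal mixed models will be used to analyze repeated measurements at baseline, 8 weeks, and 12 weeks". The Power Analysis gives power 0.80 at two-sided 0.05 for 38 people, effect size 0.549 and 25% attrition.

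**Attrition.** The plan does respond to it. Under Attrition Analyses: "Preliminary analyses will determine factors that are associated with attrition effects", with differential loss examined by covariates such as age and gender. Specific Procedures lists retention measures and adds: "Individuals who drop out of the intervention, and who agree, will be followed up with outcomes assessments over the same 3-month time period". Participant privacy says that data collected before withdrawal stay in the analysis. No section gives an analysis set, a missing-data rule or a sensitivity analysis for the main test.

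**H3.** Hypothesis 3 reads: "At least 75% of participants will find iTAB-CV acceptable based on exit interviews". The Data Analysis plan lists "treatment acceptability/satisfaction by questionnaire and exit interviews" among the secondary measures. In Table 1 the row "Participant acceptability/satisfaction/feasibility/exit interviews" is marked only at Visit 2 (week 12). iTAB-CV itself starts at the week-4 baseline visit ("phone given at this time").

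**The concern.** A paired test from baseline to week 12 leaves out anyone without a week-12 value, including people who supplied a week-8 value. The attrition analyses describe who leaves, but they do not adjust the H1 estimate. Follow-up after dropout reaches only those who agree. If the people lost gained less, the completers' mean change overstates the change among everyone who started the intervention. The plan says its estimates will inform the design of a later controlled trial, so the size of the estimate matters as well as its p-value.

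For H3 the problem is one of definition. Participants could mean everyone enrolled, everyone who started iTAB-CV, or everyone interviewed. With losses near the planned level these give clearly different rates, and the choice can decide whether the 75% target is met. As written, that choice could be made after the data are seen.

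**Working it through.** **Inputs.** From Power Analysis: mean change 21.7 points, SD of change 39, effect size 0.549, N = 38, attrition 25%, two-sided alpha 0.05. From Hypothesis 3: target 75%. Assumptions: 28 people observed at week 12; 38, 34 or 30 people starting iTAB-CV (34 and 30 allow for people lost in the run-in, who never start); and the mean change *g* among starters without week 12, which the documents do not give.

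**Step 1: reproduce the plan's figure.** 38 × 0.75 = 28.5, so 28 pairs. Paired t-test power from the noncentral t distribution at effect size 0.549 is 0.7997 for n = 28, 0.814 for n = 29 and 0.909 for n = 38. The stated 0.80 is therefore a completers-only figure with 28 pairs.

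**Step 2: precision among completers.** SE = 39/√28 = 7.37. The 95% half-width is 15.1. For a mean of 21.7, p = 0.0066.

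**Step 3: H1 mean among starters.** Mean = (28 × 21.7 + (N − 28) × g)/N, where 28 × 21.7 = 607.6.

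| g among the missing | N = 38 | N = 34 | N = 30 |
|---|---|---|---|
| 21.7 (as completers) | 21.7 | 21.7 | 21.7 |
| 10.85 (half) | 18.8 | 19.8 | 21.0 |
| 0 | 16.0 | 17.9 | 20.3 |
| −10 | 13.4 | 16.1 | 19.6 |

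At zero gain the shifts are 5.71, 3.83 and 1.45 points. Divided by 7.37 these are 0.77, 0.52 and 0.20 SE. At −10 with 38 starters the shift is 8.34 points, or 1.13 SE.

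**Step 4: significance.** The method is multiple imputation from the completers' distribution, with imputed values shifted to mean g and no auxiliary data. At zero gain p is about 0.047, 0.027 and 0.012 for 38, 34 and 30 starters. With 38 starters it is about 0.052 at −1 point (the threshold is crossed about there) and 0.10 at −10 points. Filling in one fixed value per missing person misleads because it shrinks the SD: with 38 starters, half-gain fill gives p = 0.0014, stronger than the completers' 0.0066.

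**Step 5: H3.** Take 21 acceptances among 28 interviewed: 75%, exact 95% CI 55% to 89%.

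| | 38 starters | 34 starters | 30 starters |
|---|---|---|---|
| Rate if the missing accept equally | 75% | 75% | 75% |
| Rate if they accept at half that rate | 65% | 68% | 73% |
| Rate if none accept (21/N) | 55% | 62% | 70% |
| Ceiling if non-interviewed count as not accepting (28/N) | 73.7% | 82.4% | 93.3% |
| Acceptances needed for 75% of starters | 29 (impossible) | 26 of 28 | 23 of 28 |

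**The case against.** **Leaving the intervention is not the same as missing week 12.** Dropouts who agree are still assessed, and acceptability is listed among the outcome measures, so some of them can enter both the paired test and the exit interview. The 25% is a planning figure and may include run-in losses. This stands: missing pairs among starters may be fewer than 10.

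**The H1 shift is modest.** At zero gain it is at most 5.7 points against a half-width of 15.1, in an uncontrolled pilot of 38 people. This also stands, and it makes the H1 part a concern about the estimate rather than a fatal flaw.

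**Much of the remedy is already planned.** This is true of the mixed model, but it is labelled exploratory and no week-12 contrast is named. Nor would the model remove bias if leaving depends on unobserved outcomes, and its week-8 values precede stage two of iTAB-CV.

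**Stronger readings that the documents do not support.**
- A reader might infer that H1 and H3 both lean favourable. H3 does so only if interviewees are the denominator and those not interviewed accept less. Counting the non-interviewed as not accepting makes the rate lean the other way. The plan says neither.
- A reader might infer that people without week-12 data do worse. The plan notes poor clinic attendance in this population and that texts may annoy, but it gives no outcome for people lost.
- A reader might take the zero-gain results as proof that significance is safe. Nothing in the documents makes zero the lower limit, and with 38 starters a slight worsening is enough to cross 0.05.

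**Conclusion.** The point holds in a limited form and should be addressed; neither the design nor the sample size is invalidated.

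**H1:** the main test discards collected week-8 data from people without week 12 and has no sensitivity analysis. The direction of any bias is conditional. With 28 of 38 starters observed and zero gain in the rest, the estimate falls from 21.7 to 16.0 points. Carried into the later trial at the same SD, that would mean about (21.7/16.0)² = 1.8 times the sample size. With fewer starters or fewer missing pairs the effect is smaller, and it is nil if the missing change as completers do. Significance is not assured, but neither is its loss shown.

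**H3:** this is the firmer half, because the denominator is undefined whatever the missing people think. At 28 interviewed, the same 21 acceptances meet the target among interviewees and miss it among 38, 34 or 30 starters if none of the others accept.

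The figures rest on 28 observed, the assumed starter counts, the plan's 21.7 and 39 applying to completers, and the stated scenarios for the missing.

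**What to change.** 1. **H1.** Keep the paired t-test. Prespecify beside it the week-12 minus baseline contrast from the planned mixed model, with visit as a categorical term and everyone with a baseline value included. Add a sensitivity range for the mean change among starters, running from the completers' gain through zero to some worsening. If a test is wanted in those scenarios, use shifted multiple imputation, not single-value fill.
2. **H3.** State in advance which denominator decides the 75% target. Report acceptability among those interviewed and among all who started iTAB-CV, counting the non-interviewed as not acceptable in the second rate, and give the number not interviewed. Say that the starter-based rate partly measures retention and has a ceiling (73.7% with 28 of 38 interviewed, so the target could not be met). Report the self-report questionnaire separately on the same denominators.

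The cost is some analysis-plan wording, one model contrast, a short sensitivity table and a less favourable second H3 figure. No new visits are needed.
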